#### **Patients**

Patients will be consecutively recruited at the RTU, Gjøvik and St. Olavs hospital.

#### **The inclusion criteria are:**

- $\geq 65$  years of age
- confirmed cancer diagnosis (histology/cytology)
- living in one of the participating municipalities in the catchment area of SI or in the municipality of Trondheim
- referred for palliative or curative RT
- fluency in Norwegian, orally and in writing
- ability to fill in self-report questionnaires
- provide written informed consent

#### **The exclusion criteria are**

- severely ill with a life expectancy  $< 3$  months
- referred to receive one fraction of RT only (one day treatment)

### **Adjustment of inclusion criteria**

Bullet point two “confirmed cancer diagnosis (histology/cytology” is changed to: “Confirmed cancer diagnosis (preferably histologically or cytologically, but patients referred for radiotherapy for cancer based on medical history, imaging and blood analyses are also eligible»

Otherwise, there are no changes to the inclusion and exclusion criteria.

### **Adjustment of timing for baseline registrations**

---

According to original protocol, amendment 1, page 16, baseline registrations should be completed within the second day of treatment. We have realized that this is not feasible for all patients due to practical constraints. The patients often have several appointments during the first period of treatment like seeing their oncologist and/or cancer nurses, and are also often in short of time to be able to comply with scheduled transportation. As this study is not only a pilot study testing the potential effect of the intervention program, but also a feasibility study,

these circumstances have to be taken into account to enable inclusion of all patients who potentially may benefit from the intervention program. Thus, we have decided on the following:

- Patients who receive a radiotherapy regimen with less than 15 fractions (short term treatment, usually 10 fractions or less) should have their baseline registrations completed by the third day of treatment
- Patients who receive radiotherapy with 15 fractions or more (long term treatment) should have their baseline registrations completed within the sixth day of treatment

As any negative impact of radiotherapy generally occur by the end of treatment, we believe that these changes would not have any effect on the registrations or our results.

## **Amendment B**

### **Revision of sample size estimate 09.03.20**

#### **The original estimates as stated in Amendment 8 (12-03-19) were as follows:**

Sample size estimations are based on a block-randomized cluster RCT. A total of 53 patients distributed in 16 clusters (proportionally to cluster size) in each group will enable the detection of a clinically significant difference (12 points) in the physical functioning QLQ-C30 scale at week 8 with a standard deviation (SD) of 24 in each group at the significance level of 5% and a power of 80%, given an intra-cluster correlation (ICC) of 10%. The ICC is assumed to be small as the intervention primarily will be applied by municipal cancer nurses with similar training in collaboration with hospital specialists, similar to all intervention patients. Power calculation was performed for analysis of covariance, adjusting difference between groups for baseline values, and assuming the correlation between baseline and follow-up measurements to be 0.5. According to a former study on older cancer patients by this study group, we expect an attrition of about 15-20% at 16 weeks of follow-up post-RT. Furthermore, it is paramount to ensure that all municipalities are represented by included patients. To take this and attrition into account, we aim at increasing sample size by about 28% and including 81 patients in each group, i.e. a total of 162 patients.

#### **Revision of estimates**

##### **Background:**

The present study is a block cluster-randomized study where 32 municipalities/city districts have been allocated to either control or intervention using a computer generated code. Due to large differences in number of inhabitants between municipalities/city districts, the

---

 Amendment 09-03-20. Improving function and quality of life for older cancer patients receiving radiotherapy, a randomized controlled pilot study

randomization units were stratified according to number of inhabitants prior to randomization (5 strata). Based on strata sizes and the estimated sample size, the preplanned number of study participants varied from 2 to 16 in different strata (as explained in the original application to the Ethical Review Board, attachment 7).

Before embarking on the study, the following considerations were made (Original protocol amendment 5, page 34 -35):

- the enrolment was estimated to take one year
- the number of eligible patients referred for radiotherapy from each randomized unit would depend on/vary according to chance
- there was a risk that there would not be enough eligible patients from the small municipalities to enable inclusion of the pre-planned number
- it was thus likely that it would be necessary to increase the number of patients from some municipalities (most likely the larger ones), and reduction in number of strata would also require a larger number of patients

### **Current status of inclusion**

Based on these considerations, the inclusion rate, in particular the inclusion from each municipality, has been continuously monitored.

By the 25th of February 2020, the status was:

- a total of 111 patient were included
- one of the municipalities has withdrawn before including any patient
- another four municipalities with preplanned two patients had not included any of the patients so far
- in five other randomized smaller municipalities with preplanned two patients for inclusion, only one patient had been included from each so far

This implies that the number of strata will be seriously reduced. Hence, sample size has to be adjusted correspondingly. Furthermore, to be able to include a required number of patients according to the new estimates the period for recruitment has to be extended.

### **New sample size estimate**

The revised sample size estimate is based on the same end-point, assumed difference and SD estimates as well as requirements for significance and power as the original. However, due to the reduction in number of strata and smaller number of patients than preplanned from some strata, the new estimate indicates that at least 69 patients must be included in each trial arm. Considering attrition, as described for the original sample size estimates, we now estimate that a total of 186 patients, i.e. 93 patients in each trial arm, will be required to show the statistically significant difference between groups given it exists.

## **Conclusion:**

We aim at including a total of 186 patients, i.e. 24 patients more than originally estimated. It also means that more patients than preplanned will have to be included from some of the participating municipalities, i.e. from those that during the inclusion period present with eligible patients.

For the analysis of the primary outcome, however, we need at least 138 evaluable patients, i.e. patients where the primary outcome is registered. Thus, by closely monitoring the inclusion and response rate, it may be possible to stop the enrolment before the end of Sep 2020, and before we reach 186 patients. We may also need to enroll more than the estimated 186 patients to reach the target number of evaluable patients, and in this case, a new application to the Ethical Review Board will be submitted.

**To be noted:** Due to the increase in sample size, the inclusion period was extended primarily to Sep 2020. However, study recruitment had to be paused in March 2020 due to the covid pandemic, and was thereafter opened again in the autumn 2020, please see published protocol paper .

Protocol amendment - 12-03-2019

Plan for statistical analyses – revised and specified

The effectiveness of the intervention will be tested by the use of patient-reported measures and tests for physical performance/mobility. Additionally, feasibility will be evaluated and the use of health care services and cost-effectiveness will be registered and evaluated. The pre-defined primary time point for outcome assessment is 8 weeks post-RT.

Primary outcome – Physical Functioning measured by the European Organisation for Research and Treatment of Cancer (EORTC) Quality of life Questionnaire-C30 (QLQ-C30)¹

Secondary outcomes are:

- global health assessed by the EORTC QLQ-C30 global health/quality of life subscale (question 29 and 30)
- health related quality of life (HRQoL) assessed by EQ-5D-5L²
- physical performance/mobility assessed by the following performance tests: Short Physical Performance Battery (SPPB)³, grip strength (measured by a dynamometer),⁵
- cost-effectiveness: the incremental cost-effectiveness ratio (ICER) i.e. the difference in mean costs divided by the difference in mean Quality Adjusted Life Years (QALYs)
- use of health care services (hospital in- and outpatient services and municipality services in terms of home care, nursing home care and use of other services such as general practitioner, physiotherapist, occupational therapists, and rehabilitation programs)
- feasibility at patients' and organizational level, see "Feasibility, page 3"

Other pre-defined outcomes:

- mobility assessed by the Timed Up and Go test,⁴ and one-legged balance test⁶
- symptom occurrence assessed by the EORTC QLQ-C30, specifically fatigue, pain, dyspnea, and sleeping disturbances
- emotional function assessed by the EORTC QLQ-C30
- nutritional abnormalities assessed by BMI, weight loss and loss of appetite (subscale of the EORTC QLQ-C30).

Primary analysis

Primary analysis will assess the difference between the control and the intervention groups in physical function measured by the EORTC QLQ-C30 questionnaire at 8 weeks after baseline. Longitudinal analysis of covariance will be performed by estimating a linear mixed model with fixed effects for baseline values, time and interaction between time and group variable. The model will include random effects for patients nested within study cluster.

Secondary analyses

The difference between the control and the intervention groups in the secondary outcomes global health (assessed by the EORTC QLQ-C30 questionnaire global health/global QoL subscale), HRQoL (assessed by the EQ-5D-5L), SPPB scores and grip strength at 8 weeks after baseline will be assessed by the same method as described for the primary analysis.

Furthermore, the differences between the control and the intervention groups in trend in the primary outcome physical functioning and all continuous secondary outcomes throughout the follow-up period (assessment points by the end of RT, and 4, 8, 16, 32 and 52 after RT) will be assessed by linear mixed model with fixed effects for baseline values, time and interaction between time and group variable. The model will include random effects for patients nested within study cluster. Differences between groups in dichotomous outcomes will be assessed by generalized linear model with the same fixed and random effects as described above.

Primarily, all analyses will be performed on intention-to-treat principle. As sensitivity analysis, per-protocol approach will be conducted as well.

We will also use the statistical approach as described for the primary and secondary analyses to compare the intervention group to a retrospective, matched controlled group from a foregoing observational study (NCT03071640/ 2016/2031 REK sør-øst A). These analyses will focus on the primary endpoint in this pilot study, i.e. physical function, and the secondary outcomes global QoL (from the EORTC QLQ-C30 questionnaire), Timed Up and Go and symptom occurrence.

Other analyses

Quantitative data will be presented by suitable descriptive statistics. Distributions of continuous outcomes will be inspected graphically by assessing the histograms. Model assumptions will be assessed by established methods. In the case of violation of assumptions necessary adjustments will be implemented.

Exploratory analyses

Following the main primary and secondary analyses, the data will be explored further to identify possible groups of patients following different trajectories of physical function, global quality of life and other relevant outcomes, and patient characteristics associated with favourable development in the defined outcomes.

Economic evaluation

We will calculate the intervention cost based on a micro-costing approach. Cost-effectiveness of the intervention will be evaluated by calculating the incremental cost-effectiveness ratio (ICER) that is the difference in mean costs divided by the difference in mean Quality

Adjusted Life Years (QALYs). We calculate QALYs by an area under the curve approach under the assumption of piecewise linear change in EQ-5D-5L-index values over time. Missing data will be imputed by multiple imputation and the uncertainty of the ICER will be assessed by performing sensitivity analysis including application of bootstrapping techniques.

Feasibility

Feasibility will be assessed by a process evaluation aiming to identify facilitators and barriers for a successful implementation, using mixed methodology. Measures recommended for each patient's intervention plan will be consecutively registered, as will patient's compliance and adherence through weekly contact with the coordinating nurse (log notes). Further data will include interviews with patients and providers. Questionnaires to involved primary health care nurses and other relevant professionals will also be used.

Sample size

Sample size estimations are based on a block-randomized cluster RCT. A total of 53 patients distributed in 16 clusters (proportionally to cluster size) in each group will enable the detection of a clinically significant difference (12 points)⁸ in the physical functioning QLQ-C30 scale at week 8 with a standard deviation (SD) of 24 in each group at the significance level of 5% and a power of 80%, given an intra-cluster correlation (ICC) of 10%. The ICC is assumed to be small as the intervention primarily will be applied by municipal cancer nurses with similar training in collaboration with hospital specialists, similar to all intervention patients. Power calculation was performed for analysis of covariance, adjusting difference between groups for baseline values, and assuming the correlation between baseline and follow-up measurements to be 0.5. According to a former study on older cancer patients by this study group, we expect an attrition of about 15-20% at 16 weeks of follow-up post-RT. Furthermore, it is paramount to ensure that all municipalities are represented by included patients. To take this and attrition into account, we aim at increasing sample size by about 28% and including 81 patients in each group, i.e. a total of 162 patients.

References

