## **Design**

---

[figure not shown]
The present study is a controlled cluster-randomized pilot study. Cluster-randomization is chosen to avoid contamination of the control group. It is paramount that control and intervention patients are not handled by the same primary health care professionals, and this can only be achieved by randomizing municipalities (or health care districts).

Before patient recruitment commences, a selection of 32 municipalities/city districts (= clusters) will be stratified into blocks in accordance with number of inhabitants. The selection will include city districts, large and smaller municipalities to ensure sample size and representativity. Clusters within each block will be randomly assigned to one of the groups by using a computer-generated code, 16 in each group.

Eligible patients from clusters assigned to intervention will enter the intervention group and enter the intervention program. Patients from control clusters will enter the control group.

These patients will receive treatment and care in accordance with usual routines and standards

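### The SAP's mixed models omit the five population-size strata used to randomise clusters; if those strata predict outcome beyond baseline, the test is conservative and loses power.

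*SAP*

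**What the plan says.** The protocol's Design section says that clusters "will be stratified into blocks in accordance with number of inhabitants" and are then allocated at random within each block, 16 to each arm. Amendment B (9 March 2020) confirms that the "randomization units were stratified according to number of inhabitants prior to randomization", gives the number of strata as five, and adds that "the preplanned number of study participants varied from 2 to 16 in different strata".

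The SAP's Primary analysis specifies a "linear mixed model with fixed effects for baseline values, time and interaction between time and group variable", with random effects for patients nested within cluster. Secondary analyses repeat these terms for the continuous outcomes and for the trends, and dichotomous outcomes get a "generalized linear model with the same fixed and random effects as described above". No SAP model contains stratum or block.

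The SAP's Sample size section describes a block-randomised cluster trial, but "Power calculation was performed for analysis of covariance, adjusting difference between groups for baseline values" and for nothing else. The protocol's Statistics section promises further adjustment for relevant covariates without naming any, and the SAP does not take this up.

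**The concern.** Randomising within strata forces the arms to be balanced on population size, so differences between strata do not add to the true variance of the group comparison. A model without strata does not know this. It attributes those differences to the cluster random effect and carries them into the standard error of the group difference. If population size is prognostic given baseline, the reported standard error is too large, the test rejects less often than 5% under the null, and power is lost. The benefit of stratifying is then discarded at the analysis stage.

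There is little power to spare. Amendment B revised the requirement so that "at least 69 patients must be included in each trial arm", after one municipality had withdrawn and "another four municipalities with preplanned two patients had not included any of the patients so far". The stratum is already known for every cluster.

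**Working it through.** **Inputs from the documents.** Difference 12 points, SD 24, baseline correlation 0.5, 5% significance (two-sided assumed), ICC 0.10 (SAP, Sample size). The protocol's Sample size section uses ICC 0.05, so both values are run. Evaluable patients: 69 per arm (Amendment B). Clusters: 32 − 1 withdrawn − 4 without patients = 27, or k = 13.5 per arm, as at 25 February 2020.

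**Assumption.** s is the share of cluster variance that lies between strata. The documents give no value; 0 to 0.5 is shown.

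**The plan's own figure.** Without clustering, n = 2 × (24 × (1.960 + 0.842)/12)² × (1 − 0.5²) = 47.1 per arm. With 16 equal clusters, n = 47.1 × (1 − ICC)/(1 − 47.1 × ICC/16). This gives 60.1, so 61, at the stated ICC of 0.10, and 52.5, so 53, at ICC 0.05. The SAP's 53 is therefore reproduced only with ICC 0.05. That is a separate matter and does not affect this point.

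**Formula check.** Residual variance = 24² × (1 − 0.5²) = 432.

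- Variance the unadjusted model reports: 2 × 432 × [(1 − ICC)/69 + ICC/k]
- True variance under stratified allocation: 2 × 432 × [(1 − ICC)/69 + ICC × (1 − s)/k]
- Degrees of freedom: 2k − 2 unadjusted, 2k − 6 with four stratum terms; power from the noncentral t.

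At ICC 0.10 and k = 13.5 the reported variance is 864 × (0.01304 + 0.00741) = 17.67, so SE 4.20. At s = 0.5 the true variance is 864 × (0.01304 + 0.00370) = 14.47, so SE 3.80.

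| ICC | s | SE reported | SE true | Power without strata | Power with strata | Size without strata |
|---|---|---|---|---|---|---|
| 0.10 | 0 | 4.20 | 4.20 | 78.3% | 77.7% | 5.0% |
| 0.10 | 0.10 | 4.20 | 4.13 | 78.7% | 79.2% | 4.6% |
| 0.10 | 0.25 | 4.20 | 4.01 | 79.3% | 81.4% | 4.1% |
| 0.10 | 0.50 | 4.20 | 3.80 | 80.5% | 85.3% | 3.2% |
| 0.05 | 0 | 3.89 | 3.89 | 84.3% | 83.8% | 5.0% |
| 0.05 | 0.10 | 3.89 | 3.84 | 84.6% | 84.5% | 4.8% |
| 0.05 | 0.25 | 3.89 | 3.78 | 84.9% | 85.7% | 4.4% |
| 0.05 | 0.50 | 3.89 | 3.67 | 85.6% | 87.6% | 3.9% |

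Adjustment breaks even at s of about 0.06 for ICC 0.10, which is a between-stratum SD of √(0.06 × 43.2) = 1.6 points. For ICC 0.05 it breaks even at about 0.11, or √(0.11 × 21.6) = 1.5 points. With all 16 clusters per arm and ICC 0.10 the pattern is the same: 81.2% to 80.8% (s = 0), 82.1% to 83.9% (s = 0.25), 83.1% to 87.1% (s = 0.5).

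**Simulation with unequal clusters.** Week-8 random-cluster model fitted by REML, 20,000 runs per cell. Assumed layout per arm: 14 clusters and 69 patients in five strata (five clusters of 2, three of 3, three of 5, one each of 9 and 10, one of 16). Power without and with strata:

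| s | ICC 0.10 | ICC 0.05 |
|---|---|---|
| 0 | 74.1%, 73.3% | 81.0%, 80.3% |
| 0.10 | 75.0%, 75.1% | 81.7%, 81.1% |
| 0.25 | 75.6%, 77.7% | 81.6%, 81.9% |
| 0.50 | 76.5%, 80.9% | 82.9%, 84.6% |

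The mean estimate was 12.0 throughout, so neither model is biased. At ICC 0.10 and s = 0.5 the size was 3.5% without strata and 4.9% with them.

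**Second simulation.** Stratum variance was added on top of a residual ICC of 0.10 (32 clusters, 136 patients, assumed layout, 3,000 runs). At a stratum SD of 0, power was 76.7% without and 75.6% with strata; at an SD of 3 points, 73.9% and 75.8%. SDs of 6 and 9 cost about 10 and 21 points of power without strata, but imply total ICCs of (43.2 + 36)/(432 + 36) = 0.17 and (43.2 + 81)/(432 + 81) = 0.24, well above the plan's values. Those two losses are not relied on here.

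**The case against.** The case for leaving the model alone has several parts.

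- **The gain is conditional.** The documents nowhere call population size prognostic. Stratification is explained by the large differences in cluster size, baseline is already in the model, and cluster variation is expected to be small. At ICC 0.05 there is little to gain unless s is large. This stands, and it limits the size of the point.
- **The gain is only recalibration.** In a rerun with critical values set to exactly 5%, adjustment changed power by −1.3 to +0.2 points. That describes the mechanism correctly: adjustment restores the nominal size. But s is unknown, so the unadjusted test cannot be recalibrated in practice, and including stratum is how the analysis achieves it.
- **Adjustment can slightly exceed 5%.** In the first simulation at ICC 0.10, size moved from 5.1% to 5.7% at s = 0.10 and from 4.5% to 5.3% at s = 0.25. The model without strata also reached 5.6% at s = 0, so this is a general small-sample degrees-of-freedom issue rather than a cost of the stratum term.
- **The layout is assumed.** Clusters per stratum are not given, 27 clusters is an interim count, and Amendment B expects strata to be lost. This is why a merging rule is needed. The direction of the result is the same with 27 or 32 clusters.
- **The protocol already allows covariates.** It does, but permission to adjust for unnamed covariates does not place stratum in the pre-specified model.
- **Dichotomous outcomes were not calculated.** This stands. In a logistic mixed model the stratum term also changes the conditional effect being estimated, and sparse strata can be unstable.

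**Conclusion.** The concern holds. The analysis does not reflect the stratified randomisation. This is a question of efficiency and of a correct standard error, not of validity: there is no bias and no inflation of false positives.

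Under the plan's ICC of 0.10, adding strata is worth about 2 points of power if a quarter of the cluster variance lies between strata and 4 to 5 points if half does. At ICC 0.05 the corresponding gains are under 1 point and about 2 points. If strata carry nothing, adjustment loses 0.4 to 0.8 points in the formula and the first simulation, and 1.1 in the second. All of this rests on an assumed s, an assumed spread of clusters over strata, and a week-8 linear model rather than the full longitudinal one. The change is worth making because the possible gain exceeds the bounded loss and nothing has to be collected.

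**What to change.** In the SAP, add randomisation stratum as a fixed effect to the primary and secondary linear mixed models for the randomised comparison. State beforehand that adjacent strata are merged if one retains no cluster in an arm. Apply the same rule to the models for dichotomous outcomes, noting that the estimated effect is then conditional on stratum.

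As a clarification only, state that time is a categorical factor with a group effect at every visit, and that the primary estimate is the group difference at 8 weeks post-RT, the time point named in the SAP's opening paragraph. With time coded this way, the missing group main effect is harmless.

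The cost is a few sentences of SAP wording and up to four cluster-level degrees of freedom. The change should be fixed before outcomes are compared by arm, because choosing it afterwards would be open to challenge.

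### The mixed models give baseline one slope for all visits, so its adjustment drops out of between-visit trend contrasts; a baseline-by-visit term would restore it (minor, secondary analyses)

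*SAP*

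**What the plan says.** Under Primary analysis the SAP states that "Longitudinal analysis of covariance will be performed". The method it gives for this is "estimating a linear mixed model with fixed effects for baseline values, time and interaction between time and group variable". Under Secondary analyses it first applies the same method to the week-8 differences in the secondary outcomes. It then adds a separate target, the difference between groups in trend, which "will be assessed by linear mixed model with fixed effects for baseline values, time and interaction between time and group variable". The visits given for that model are "assessment points by the end of RT, and 4, 8, 16, 32 and 52 after RT", so baseline is a covariate and not an outcome visit. The random part is also stated: "The model will include random effects for patients nested within study cluster".

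Three things are not stated: whether time is categorical or linear, whether a group main effect is included, and which contrast is the difference in trend. No baseline-by-time term is listed. The SAP's Sample size section uses a single baseline to follow-up correlation ("assuming the correlation between baseline and follow-up measurements to be 0.5") with no pattern over visits. The Protocol's Statistics section likewise says that trends will be compared between the groups.

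**The concern.** A main effect of baseline adds the same amount to each of a patient's visits. It therefore vanishes from any within-patient change, and so from any difference between the group effect at one visit and the group effect at another. A model described as an analysis of covariance would then give a trend comparison that makes no use of baseline.

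This matters only if baseline predicts the visits unequally well, which is plausible here. The Protocol's amendment on timing of baseline registrations describes short courses of usually ten fractions or fewer, with baseline completed by the third treatment day. With one fraction per weekday (an assumption), baseline and end of RT can then be under two weeks apart, while week 52 is a year later. If predictive strength falls over time, an arm that starts better by chance will tend to show a worse trend, and the reverse. The trend estimate is also less precise than the collected data allow.

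**Working it through.** The plan states no figure for this point, so there is none to reproduce.

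**Inputs.** SD 24, ICC 0.10 and correlation 0.5 come from the SAP's Sample size section. The cluster layout is an assumption: 14 clusters of 5 per arm. It is close to the 69 evaluable patients per arm in Amendment B and to 32 − 1 − 4 = 27 clusters that had recruited or were not reported empty at the February 2020 status. All decay patterns below are assumptions.

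**Algebra.** With categorical time and only the listed terms, E[Y_ij] = a_j + b·Y_i0 + d_j·G_i. Each d_j is a group difference at visit j, adjusted through the pooled slope b. For two visits, E[Y_ij − Y_ik] = (a_j − a_k) + (d_j − d_k)·G_i, and b is gone. Let the true slopes be b_j and the baseline difference between arms D. With complete data and a patient random intercept, the pooled slope is the mean of the b_j, so

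- error in the visit-j difference = (b_j − b_mean)·D
- error in the between-visit contrast = (b_j − b_k)·D

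**Size of chance imbalance.** SE(D) = 24 × √(2 × (1 + 4 × 0.10)/70) = 24 × √0.04 = 4.8 points. With 69 patients in 16 clusters per arm it is 24 × √(2 × 1.331/69) = 4.7. With the Protocol's SD 22 and ICC 5% it is 22 × √(2 × 1.2/70) = 4.1.

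**Steep decay: 0.7, 0.6, 0.5, 0.45, 0.35, 0.3** (equal SDs at all visits, so correlation = slope)

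- Week 52 minus end of RT: 0.3 − 0.7 = −0.40 per point of imbalance, or 1.9 points at 1 SE.
- Least-squares line through the six values against weeks 0, 4, 8, 16, 32, 52: slope −13.73/1973.3 = −0.00696 per week, × 52 = −0.36. Simulation of 4,000 trials gave −0.37, or 1.8 points at 1 SE and 3.5 at 2 SE.
- Precision: adding baseline-by-visit cut the SE of the trend from 4.0 to 3.6. The rounded SEs give 1 − (3.6/4.0)² = 19%; the simulation gave 18%.
- Week 8, all six visits fitted: b_mean = 2.9/6 = 0.483, so (0.5 − 0.483) × 4.8 = 0.1 point. With visits only to week 8: (0.5 − 0.6) × 4.8 = −0.5 point. The milder pattern gives about 0.2.

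**Milder decay, 0.6 to 0.4:** −0.15 per point on the linear trend, 0.15 × 4.8 = 0.7 point at 1 SE, 2% of variance recovered. **Constant correlation:** nil.

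**Separate simulation** (300 trials per scenario, 69 patients and 16 clusters per arm, six visits, no true effect, baseline imbalance set at 6 points, complete data). Mean estimates:

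| Baseline slope | Model | Week 8 | Week 52 | Week 52 − end RT |
|---|---|---|---|---|
| Constant 0.5 | SAP terms | 0.02 | 0.18 | −0.09 |
| Constant 0.5 | no baseline | 2.96 | 3.13 | −0.09 |
| Constant 0.5 | + baseline-by-visit | 0.03 | 0.19 | −0.08 |
| Falling 0.8 to 0.3 | SAP terms | 0.32 | −1.31 | −3.08 |
| Falling 0.8 to 0.3 | no baseline | 3.56 | 1.94 | −3.08 |
| Falling 0.8 to 0.3 | + baseline-by-visit | 0.03 | 0.19 | −0.08 |

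The last column is identical with and without baseline, as the algebra says, and agrees with 6 × (0.3 − 0.8) = −3.0. The first two outcome columns show that the adjustment does work for single-visit differences. With dropout the cancellation is near rather than exact (−2.85 against −2.88).

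**Linear time.** With the listed terms and no group main effect, baseline does not cancel (constant slope: trend to week 52 of 0.04 with it, 0.64 without). With a group main effect added, it cancels exactly (0.00 and 0.00). Under the falling slope, the listed terms give −2.53, the version with a group main effect −2.77, and baseline-by-time 0.05 and 0.01 respectively.

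**The case against.** A reader might infer that the comparisons to week 52 are not adjusted for baseline at all. The documents do not support that. No group main effect is listed, so with categorical time each time-by-group coefficient is a baseline-adjusted visit difference. The week-8 and week-52 differences in the table confirm it. The cancellation belongs to between-visit contrasts, and to a linear-time model only if a group main effect is added.

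A reader might also infer bias or an inflated error rate. Allocation is randomised, so imbalance is a matter of chance and averages out. Under steep decay, with SEs of 4.0 and 3.6, a nominal 5% trend test rejects about 12% of the time at a 2-SE imbalance, but about 5% at 1 SE and 3% at perfect balance. Averaged over randomisations it stays near 5%. An imbalance of 2 SE or more arises in about 5% of trials.

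The decay is not in the documents either: the SAP gives one correlation of 0.5, for which nothing is lost. The count of 27 clusters is an interim status. Under the Protocol's Outcomes and assessments, performance tests stop at week 16, so the 52-week figures concern patient-reported scales only. All of this stands and keeps the point small.

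Finally, the SAP's Other analyses promise model checks: "In the case of violation of assumptions necessary adjustments will be implemented". A common baseline slope is such an assumption, but it is not named, and adding the term after seeing the trends would be post hoc.

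**Conclusion.** The point holds as a minor improvement to the secondary trend analyses. The primary week-8 estimate is essentially unaffected: 0.1 to 0.5 point at a 1-SE imbalance under the assumed decay, against a target difference of 12.

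For the trend contrast, the uncorrected part ranges from nil (constant correlation), through 0.7 point (milder decay), to about 1.8 points (steep decay), each at a 1-SE imbalance of 4.8 points. The recoverable variance is nil, 2% and 18% respectively. These figures rest on assumed decay patterns, equal SDs across visits, complete data and 14 clusters of 5 per arm. They are errors conditional on imbalance and some lost precision; they are not bias in the randomised comparison.

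The comparison with retrospective matched controls, which the SAP analyses by the same approach, is more exposed. Baseline differences there are not governed by randomisation and need not average out, and the SAP does not name the matching variables.

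**What to change.** In the SAP's Primary analysis and Secondary analyses:

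- specify time as a categorical visit;
- add baseline-by-visit to the fixed effects;
- state the group terms explicitly, including whether there is a group main effect;
- define the trend contrast, for example the group difference at week 52 minus that at end of RT, or a joint test that the group differences are equal across visits;
- read the week-8 and all later differences from this model, and use it for the other continuous outcomes and for the matched-control comparison.

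For the performance tests the contrast can run only between weeks 8 and 16.

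The change takes one or two sentences and no new data. It uses up to five more degrees of freedom per model. If the slope is in fact constant, the price is slight: in the 300-trial simulation the SD of the week 52 minus end of RT contrast rose from 2.84 to 2.90, about 4% in variance at a 6-point imbalance.
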